2.0 Abbreviations

ADR	Adverse Drug Reaction
AE	Adverse Event
BASDAI	Bath Ankylosing Spondylitis Disease Activity Index
CASPAR	CLASSification criteria for Psoriatic ARthritis
CRF	Case Report Form
CRO	Clinical Research Organization
DAS28	Disease Activity Score 28
EDC	Electric Data Capture
eow	every other week
GPSP	Good Post-marketing Study Practice
GVP	Good Vigilance Practice
HAQ	Health Assessment Questionnaire
LOCF	Last Observation Carried Forward
MR	Medical Representatives
MedDRA	Medical Dictionary for Regulatory Activities
PASE	Psoriatic Arthritis Screening and Evaluation questionnaire
PASI	Psoriasis Area and Severity Index
PMDA	Pharmaceuticals and Medical Devices Agency
PMOS	Post Marketing Observational Study
PsA	Psoriatic Arthritis
PsV	Psoriatic vulgaris
RA	Rheumatoid Arthritis
SADR	Serious Drug Reaction
SAE	Serious Adverse Event
SAP	Statistical Analysis Plan
SJC	Swollen Joint Counts
TJC	Tender Joint Counts
TNF	Tumor Necrosis Factor
VAS	Visual Analog Scale
WPAI-PsA	Work productivity and Activity Impairment questionnaire:PsA

abbvie

Humira® 40 mg/0.8 ml for subcutaneous injection (generic name: adalimumab)
P15-084

4.0 Abstract

Title: Special Investigation (Working Productivity and Activity Impairment / WPAI in Japanese patients with psoriatic arthritis / PsA.)
Rationale and Background : <Background> In Japan, scientific evidence which shows improvement in WPAI-PsA with biologics is missing. <Rationale> Previous studies showed 1) significant work productivity and activity impairment in Japanese patients with psoriasis arthritis (PsA) compared to psoriasis without arthritis (M Hayashi et al. Journal of Dermatological Science 72 (2013), 2) improvements in work productivity and activity impairment after 16 weeks of adalimumab treatment for patients with psoriasis (including 25% PsA) (Alex Boer Kimball et al. J Am Acad Dermatol 2012), 3) improvements in PASI score and DAS28 (Humira® 40 mg for S.C. Injection - Study Protocol for Special Investigation in patients with Ps and PsA (All-Case study) P12-077). Accordingly, improvement of disease activity scores and WPAI-PsA scores is expected in this study of patients with PsA
Research Question and Objectives : To assess the effectiveness of adalimumab on PsA-related Overall work impairment (OWI) after 24weeks.
Study Design : Single-arm, multi-center, prospective cohort study
Population : Setting : <inclusion Criteria> Patients who have never been administered adalimumab. PsA patients meet diagnostic criteria for CASPAR criteria. They should be Paid worker (including part-time worker).

<Exclusion Criteria> Patients showing decreased basic activities of daily life such as hospitalization and bedridden. Patients with contraindications to adalimumab.	
Variables : WPAI:PsA, PASE, PASI, DAS28, Tender Joint Counts(0-68), Swollen Joint Counts(0-66), HAQ, BASDAI, Spondylitis(Yes/No), Dactylitis(Yes/No), Enthesitis(Yes/No), Nail Psoriasis(Yes/No)	
Data Sources : Data sources for collection of data in this investigation are from institute's medical charts and reports from subjects.	
Study Size : Sample size : 130 patients	
Data Analysis : All statistical analysis procedures will be described in detail in the SAP. This plan will be developed by the responsible protocol author in collaboration with CRO. The SAP shall be finalized and approved by the responsible protocol author and study-designated physician before the database is used for the final analysis.	
Milestones :	
Start of Data Collection :	01 Dec 2014
End of Data Collection :	31 Aug 2017
Study Progress Report :	Not Applicable
Interim Report :	Not Applicable
Registration in the EU PAS Register :	Not Applicable
Final Report of Study Results :	1 May 2018

5.0 Amendments and Updates

No.	Date	Section of study Protocol	Amendment or Update	Reason
1	18 Aug 2015	4.0 Abstract 6.0 Milestone -End of Data collection -Final Report of Study Results	Amendment	As of 18 Aug 2015, the enrollments are 25 cases and the mean enrollments of 3 months are 7-8 cases in a month. It is necessary to extend the registration period for nine months to enroll 130 cases.
2	18 Aug 2015	9.1 Study Design The registration period	Amendment	As of 18 Aug 2015, the enrollments are 25 cases and the mean enrollments of 3 months are 7-8 cases in a month. It is necessary to extend the registration period for nine months to enroll 130 cases.
3	18 Aug 2015	11.5 Serious Adverse Event Reporting	Amendment	FDA requirement for Humira
4	23 Feb 2016	11.7 Management and Reporting of Complaints	Amendment	FDA requirement

6.0 Milestones

Start of Data Collection :	Dec 2014
End of Data Collection :	31 Aug 2017
Study Progress Report :	Not Applicable
Interim Report :	Not Applicable
Registration in the EU PAS register :	Not Applicable
Final Report of Study results :	1 May 2018

7.0 Rationale and Background

7.1 Background

Psoriatic arthritis (PsA) is a multifaceted disease associated with psoriasis in skin, nail, chronic peripheral and/or axial arthritis, dactylitis, and enthsritis. Patients with PsA may experience significant physical, psychological, social, functional impairment and reduced quality of life. An important cytokine that activates and intensifies inflammation in PsA is tumor necrosis factor α (TNF- α). TNF- α inhibitors have been a major advance in PsA treatment, and showed significant effect on skin disease and arthritis. In Japanese guidance for use of biologics for psoriasis

(the 2013 version), TNF-a inhibitors shown to prevent the progression of joint destruction regardless of the pretreatment, should be positioned as the first-line treatment.[1]

Adalimumab which is a human monoclonal antibody inhibits the interaction of TNF- α with its receptors and suppresses the biological effect of this pro-inflammatory cytokine. In Japan, Humira® was approved for RA in 2008 and PsV (is this psoriasis?)and PsA in 2010. Humira® is administered as a subcutaneous (sc) injection at a recommended dose of 40 mg every other week after initial dosage of 80mg.

Previous studies have shown that adalimumab reduced the clinical symptoms (skin disease and arthritis) of PsA and improved health-related-quality life.

This is the first study that assesses work productivity of Japanese PsA patients being treated with adalimumab. This study is a PMOS according to GPSP/GVP, and will be conducted in compliance with the recommendations of the PMDA.

7.2 Rationale

Hayashi M, et al. reported significant WPAI in Japanese patients with PsA compared to psoriasis without arthritis [2]. Kimball A B, et al. reported improvements in work productivity and activity impairment after 16 weeks of adalimumab treatment for patients with psoriasis (including 25% PsA) [3]. Special Investigation (All cases investigation in patients with psoriasis vulgaris and psoriatic arthritis) (P12-077) showed improvements

abbvie Humira® 40 mg/0.8 ml for subcutaneous injection (generic name: adalimumab)
P15-084

in PASI score and DAS28. Accordingly, improvement of disease activity scores and WPAI-PsA scores is expected in patients with PsA.

8.0 Research Question and Objectives

Primary objective:

To assess the effectiveness in dairy clinical practice of adalimumab on PsA-related Overall work impairment (OWI) after 24weeks.

Secondly objectives:

To assess the effectiveness (PASE score, DAS28, PASI, TJC, SJC, HAQ and BASDAI) in daily clinical practice of adalimumab in PsA patients.

9.0 Research Methods

9.1 Study design

This study is a prospective, multicenter, post-marketing observational study (PMOS). For each individual patient, the PMOS starts with the enrollment at the beginning of the treatment with adalimumab.

- Observation period
- 24 weeks (or discontinuation in this study)
- Discontinuation in this study
- When adalimumab treatment is discontinued.

The study shall be terminated for the patient on the day of discontinuation of adalimumab, if the adalimumab treatment is completed prior to Week 24.

The registration period will be 2014 December to 2016 September.

9.2 Setting

Inclusion Criteria

- PsA patients meeting CASPAR criteria. The CASPAR criteria are shown in Table1 [4].
- Patients who have never been administered adalimumab.
- Patients should be paid worker (including part-time worker).

Table 1: The CASPAR criteria

To meet the CASPAR (ClASsification criteria for Psoriatic ARthritis) criteria, a patient must have inflammatory articular disease (joint, spine, or enthesal) with 3 points from the following 5 categories:

1. Evidence of current psoriasis, a personal history of psoriasis, or a family history of psoriasis. Current psoriasis is defined as psoriatic skin or scalp disease present today as judged by a rheumatologist or dermatologist.†
A personal history of psoriasis is defined as a history of psoriasis that may be obtained from a patient, family physician, dermatologist, rheumatologist, or other qualified health care provider.
A family history of psoriasis is defined as a history of psoriasis in a first- or second-degree relative according to patient report.
2. Typical psoriatic nail dystrophy including onycholysis, pitting, and hyperkeratosis observed on current physical examination.
3. A negative test result for the presence of rheumatoid factor by any method except latex but preferably by enzyme-linked immunosorbent assay or nephelometry, according to the local laboratory reference range.
4. Either current dactylitis, defined as swelling of an entire digit, or a history of dactylitis recorded by a rheumatologist.
5. Radiographic evidence of juxtaarticular new bone formation, appearing as ill-defined ossification near joint margins (but excluding osteophyte formation) on plain radiographs of the hand or foot.

† Current psoriasis is assigned a score of 2; all other features are assigned a score of 1.

Exclusion Criteria

- Patients showing decreased basic activities of daily life such as hospitalization and bedridden.
- Patients with contraindications to adalimumab.

Dosage and Administration

Humira® 40mg for S.C. Injection (generic name: adalimumab)

The dose of HUMIRA for psoriasis patients is an initial dose of 80 mg followed by 40 mg given eow, starting 2 week after the initial dose as subcutaneous injection.

The dose may be increased to 80 mg eow when the effect of treatment with 40 mg eow is insufficient.

Investigator site selection

The medical representative (MR) will fully explain the purpose and methods of the study to participating physicians in medical institutions where Humira® is used or adopted

using the implementation guidance for special investigation. Written agreement will be signed between AbbVie and each participating institution.

Study Conduct

(1) Request and contract of PMOS

The data for this PMOS will be collected from rheumatologists and dermatologists. MR will fully explain the purpose and methods of the study to participating physicians in medical institutions where Humira® is used or adopted using the implementation guidance for special investigation. Written agreement will be finalized between AbbVie and each participating institution.

(2) Study methods

- 1) An Internet-based Electric Data Capture (EDC) (including some paper-based CRF) will be used to collect the study data.
- 2) Investigators will describe information about eligible patients who are receiving or will receive Humira® during the period from the date of agreement to the end of the registration period in patient registration form.
- 3) Investigators will send the patient registration form via EDC by 14 days from the day of the first Humira injection.
- 4) The sponsor will register patients according to the information described in the sent registration form.
- 5) In the study, the enrolled patients will be observed for 24 weeks from the day of the first HUMIRA® injection. During the observational period, investigators will observe the following points:
 - ① Patients should be observed carefully for clinical course and incidence of adverse events.
 - ② Incidence of adverse events must be reported to MR without delay.
- 6) After the end of the observation period, investigators will describe information about each participant in the CRF, and send the CRF via EDC. Investigators will be requested to describe information of patients who experienced adverse events on their case report forms during the observation period and provide them to MR.
The sponsor will confirm the descriptions of the consecutive patient registration form and the CRF, and conduct reinvestigation whenever necessary.

Humira® 40 mg/0.8 ml for subcutaneous injection (generic name: adalimumab)
P15-084

Registration form

Investigator site, name, patient's agreement to treat, date of the first Humira injection, date of birth or age, Patient's identification number, sex, outpatient/inpatient, history of Humira injection, CASPAR criteria (Yes/No), working situation, Humira contraindications, Testing for tuberculosis (presence/absence of the implementation of Tuberculin skin test or Interferon- γ release assay or Plain chest X-ray or Chest CT), Hepatitis B virus marker test (presence/absence)

Case Report Form

1) Patient characteristics

Patient's identification number, sex, presence/absence of pregnancy/breast-feeding and gestation (in the case of women), body weight, body height, reason for use, outpatient/inpatient, type of psoriasis (plaque / erythroderma / pustular / guttate), working situation, disease duration (Ps / PsA), comorbidity (presence/absence, disease name), medical history (presence/absence, disease name), allergic history (presence/absence, detail), drinking history (presence/absence), smoking history (presence/absence, years of smoking), Rheumatoid Factor (positive / negative)

2) adalimumab treatment

Physician/self -injection, dosage, date of the first and the last injection

3) Reason of discontinuation of injection

4) Previous drug treatment for PsA

Presence/absence of previous drug treatment for PsA,
Biologics (every biologics that was used before),
• Reason of discontinuation, date of discontinuation
Other drugs (3 month ago from start of Humira injection)

4) Previous non-drug treatment for skin disease and arthritis of PsA

5) Current concomitant drug

Presence/absence of current concomitant, product name, route of administration, reason of use, dosage, date of first and last administration

6) Current concomitant non-drug treatment for skin disease and arthritis of PsA

abbvie Humira[®] 40 mg/0.8 ml for subcutaneous injection (generic name: adalimumab)
P15-084

7) Testing for tuberculosis or serious respiratory disease

- Tuberculin skin test
- Interferon- γ release assay
- Plain chest X-ray
- Chest CT

8) Clinical evaluation

Physician:

- PASI
- DAS28
- TJC (0-68), SJC(0-66)
- Presence/absence of spondylitis, enthelitis, dactylitis, nail psoriasis

Patient:

- WPAI:PsA
- PASE
- HAQ
- BASDAI

9) Adverse events

Presence / absence of adverse events, If present, collect nature of adverse events, date of onset, seriousness, outcome (if death, collect date and cause of death, causal relationship to Humira, autopsy), causal relationship with Humira, alternative etiology, course and treatment of adverse events, comments on causality, and laboratory findings.

Table 2: Study schedule

Activity	Visit (Week)				
	0	4	12	16	24 or Discontinue
Patient characteristics	○	—	—	—	○
Previous drug treatment for PsA	○	—	—	—	—
Previous non-drug treatment	○	—	—	—	—
adalimumab treatment	—	←————→			
concomitant drug	—	←————→			
Current concomitant non-drug treatment	—	←————→			
Clinical evaluation					
1) WPAI:PsA	○	○	○	○	○
2) PASE	○	○	○	○	○
3) PASI	○	○	○	○	○
4) DAS28	○	○	○	○	○
5) TJC (0-68), SJC(0-66)	○	○	○	○	○
6) VAS assessment by physician	○	○	○	○	○
7) VAS assessment by patients	○	○	○	○	○
8)HAQ	○	-	○	-	○
9)BASDAI	○	-	○	-	○
10) Presence/absence of spondylitis, enthelitis, dactylitis, nail psoriasis	○	—	—	—	○
Adverse events	—	←————→			

9.3 Variables

As special investigation (PMOS/non-mandatory) of HUMIRA® subcutaneous injection 40 mg syringe 0.8 mL (generic name: Adalimumab) will be performed to examine the following (1) and (2) (planned visit time; before the start of treatment, and at 4, 12, 16, and 24 weeks, 4 data collection points) in Japanese PsA patients who are engaged in paid work.

(1) Primary Endpoints

- To assess adalimumab therapeutic efficacy with Japanese PsA patients, measured by improvement in OWI score after 24weeks from baseline.

(2) Secondary Endpoint

- To assess adalimumab therapeutic efficacy and safety with Japanese PsA patients, measured by following variables;
- OWI scores (baseline, 4, 12 and 16 weeks)
- Absenteeism, Presenteeism, Activity impairment (AI) scores (baseline,4,12,16 and 24 weeks)
- PASE score (baseline,4,12,16 and 24 weeks)
- PASI (baseline,4,12,16 and 24 weeks)
- DAS28 (baseline,4,12,16 and 24 weeks)
- TJC (0-68) , SJC (0-66) (baseline,4,12,16 and 24 weeks)
- BASDAI (baseline, 12 and 24 weeks)
- HAQ (baseline, 12 and 24 weeks)
- Spondylitis, Dactylitis, Enthesitis, Nail psoriasis (Yes/No) (baseline and 24 weeks)
- Adverse events

9.4 Data sources

Data sources for collection of data in this investigation are from institute's medical charts medical charts. As this investigation is for PsA patients for proper use of Humira®, base of data sources is from carte. Participant physicians in this investigation transcribe from carte to CRF which AbbVie prepares.

9.5 Study Size

Sample size: 130patients

< Rationale for setting >

In the report by Kimball A B et al. [3], in which the effect on work productivity was examined in 557 North American patients with psoriasis (including 137 PsA patients), the change of overall work impairment (OWI) during the 16 weeks of treatment with

Humira® 40 mg/0.8 ml for subcutaneous injection (generic name: adalimumab)
P15-084

adalimumab was 13.4 ± 23.8 (mean \pm SD). In this Study, the number of subjects necessary to detect the same change of OWI score was calculated to be 87 subjects at the 0.05 significance level (two-sided) and a power of 0.80. The dropout rate up to 24 weeks from the start of adalimumab treatment of the PsA patients was about 20% during all-case study for HUMIRA® in Japanese PsV and PsA patients. And the evaluable rate of OWI was about 85% during special investigation for HUMIRA® in Japanese RA patients (P12-772). Therefore, the number of patients to be enrolled is 130 cases.

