9.7 Data Analysis

Descriptive analyses will be provided. All statistical analysis procedures will be described in detail in the SAP. This plan will be developed by the responsible protocol author in collaboration with CRO. The SAP shall be finalized and approved by the responsible protocol author and study-designed physician before the database is used for the final analysis.

1) Analysis population

The data of all documented patients will be used in the statistical analysis of efficacy and safety of HUMIRA®. The data of patients with PsA that had been treated with HUMIRA® previously will be excluded from the analysis of efficacy.

(i) Patients parameters

- Number of subjects whose registration forms are collected
- Number of subjects whose case report forms are collected
- Number of subjects for safety evaluation
- Number of subjects for efficacy evaluation

(ii) Safety parameters

- Listing of the situation of the occurrence of adverse drug reactions/infections
- Factors considered to affect the safety
Incidence of adverse drug reactions by factor of patient characteristics, etc.
- Adverse events that occur during or after administration
Listing of the situation of the occurrence of serious adverse events, etc.

Humira® 40 mg/0.8 ml for subcutaneous injection (generic name: adalimumab)
P15-084

(iii) Efficacy parameters;

- Changes in WPAI-PsA scores over 4, 12, 16 and 24 weeks
- Changes in PASE score, DAS-28, HAQ, PASI score and BASDAI over 4, 12, 16 and 24 weeks
- Rate of PASI75,90 at 12, 24 weeks
- Correlation between WPAI:PsA scores and some parameters (PASE score, DAS-28, TJC, SJC, PASI score, HAQ, BASDAI)
- Factors considered to affect the WPAI:PsA scores (listing of efficacy by patient characteristics, etc.)
- Correlation between PASE score and disease/QOL parameters (DAS-28, Tender joint counts, Swollen joint counts, PASI, HAQ, BASDAI)

2) Missing observations will be documented as missing values. Instructions for the minimum documentation required for a patient to be evaluable will be established in the SAP. All data will be analyzed on the basis of observed cases and LOCF. For the statistical analysis of data concerning the course of disease (if related to changes from baseline values), an additional approach will be followed considering only patients with complete data.

3) Level of Significance

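### Section 9.5: the 87 subjects do not follow from the change, SD, significance level and power stated with them; a one-sample t-test on those inputs needs 27, and the target of 130 can stay

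*Combined protocol and SAP*

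**What the plan says.** Section 9.5 (Study Size) draws its planning values from a report on "557 North American patients with psoriasis (including 137 PsA patients"). Over 16 weeks the change in OWI on "adalimumab was 13.4 ± 23.8", identified as mean and SD. From this, "the number of subjects necessary to detect the same change of OWI score was calculated to be 87 subjects". The criterion attached to that figure is detection "at the 0.05 significance level (two-sided) and a power of 0.80". The section then allows for about 20% dropout by week 24 and an OWI evaluable rate of about 85%, and sets enrolment at 130. It names no test, null value or formula.

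The design in section 4.0 (Abstract) is a "Single-arm, multi-center, prospective cohort study". The primary endpoint in section 9.3 (Variables) is efficacy "measured by improvement in OWI score after 24weeks from baseline". Section 9.7 (Data Analysis) opens with "Descriptive analyses will be provided", makes inferential testing conditional on its being applicable, leaves the detail to the SAP, and says "All data will be analyzed on the basis of observed cases and LOCF".

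**The concern.** Every input to the calculation is printed beside its result, so the result should be reproducible. A change of 13.4 with SD 23.8 is a standardised effect of about 0.56. With one group and a change-from-baseline endpoint, an effect of that size needs only a few dozen patients for 80% power, so 87 looks far too large for the criterion it is said to meet.

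Either 87 was obtained from different inputs or a different criterion, or it was miscalculated. In both cases the stated power does not describe the study. If the true basis was a smaller effect or a larger SD, the reader should know, because that decides whether 87 evaluable patients is a generous number or only just enough.

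**Working it through.** **Inputs.** Change 13.4, SD 23.8, two-sided α 0.05, power 0.80, dropout about 20% and evaluable rate about 85% are all in section 9.5. The single-arm design is in section 4.0 and the change-from-baseline endpoint in section 9.3. The one-sample t-test against zero is inferred from the design and endpoint, because no test is named.

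**1. Attempt to reproduce 87.** The standardised effect is d = 13.4 / 23.8 = 0.563.

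- Normal approximation: n = ((1.960 + 0.842) / 0.563)² = 24.8, so 25.
- One-sample t-test (noncentral t with n − 1 degrees of freedom and noncentrality d√n): power is 0.788 at n = 26 and 0.804 at n = 27, so 27.
- Power at n = 87 is 0.9994.

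The stated number is 87 / 27 = 3.2 times the requirement. The choice between t and z does not explain a gap of that size.

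**2. Other readings.**

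| Reading | n |
|---|---|
| Wilcoxon signed-rank, normal data (simulated; 0.801 at 28) | 28 |
| Wilcoxon signed-rank, worst-case efficiency (27 / 0.864 = 31.3) | 32 |
| Sign test, normal data (power first reaches 0.80 at 42, stays there from 47) | 42–47 |
| One-sample t-test, power 0.90 / 0.95 / 0.99 | 36 / 43 / 60 |
| Two-group t-test (not this design) | 51 per group, 102 in total |
| 23.8 as a single-visit SD, correlation 0 / 0.25 / 0.5 (SD of change 33.7 / 29.1 / 23.8) | 52 / 40 / 27 |

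None gives 87.

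**3. What would give 87.** For a one-sample t-test with n = 87 and 80% power:

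- the SD of the change would have to be about 44.1 with the change kept at 13.4; or
- the detectable difference would have to be 7.23 points at SD 23.8, which means a null value of 13.4 − 7.23 = 6.17 points instead of zero (null values of 2 / 4 / 6 points need 37 / 53 / 84).

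Two further bases come close. A 95% confidence interval with a half-width of 5 points at SD 23.8 gives (1.96 × 23.8 / 5)² = 87.04. A standardised effect of 0.30 by normal approximation gives (2.802 / 0.30)² = 87.2. The documents state none of these four. The first near match uses neither 13.4 nor a power, and the second does not use 13.4 / 23.8.

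**4. The step from 87 to 130.** 87 / (0.80 × 0.85) = 87 / 0.68 = 127.9, or 129 if rounded up at each stage, so 130 fits. In reverse, 130 × 0.68 = 88.4, about 88 evaluable. By the same rates 27 evaluable would be 27 / 0.68 = 39.7, so 40 enrolled.

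**5. Sensitivity to the SD.** The 23.8 comes from 16 weeks in a mixed psoriasis population with 137 of 557 having PsA. The week-24 SD in PsA is not known, so a range is assumed:

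| Assumed SD of change | n for 80% power at 13.4 points | Power with 88 evaluable |
|---|---|---|
| 23.8 | 27 | 0.9994 |
| 30 | 42 | 0.986 |
| 35 | 56 | 0.944 |
| 40 | 72 | 0.874 |

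With 88 evaluable and SD 23.8, the change detectable with 80% power is 7.19 points and the 95% CI half-width (t) is 5.04 points.

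**The case against.** The strongest reply is that section 9.5 names no test and section 9.7 leaves the methods to the SAP, so 27 rests on an inferred test and an undisclosed criterion is as likely as a miscalculation. The precision reading supports this: a 5-point half-width uses the stated SD, gives 87.04, and would suit a study whose analyses are descriptive. If the real basis was an SD near 44 or a null near 6 points, 87 is simply the requirement and carries no surplus.

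Much of this stands. The 27 is conditional on a one-sample t-test against zero, the near matches are real, and the surplus exists only relative to the printed inputs. But none of it rescues the sentence as written, which ties 87 to the same change of 13.4 and to power 0.80. If the basis was a precision target or an effect of 0.30, the sentence misdescribes it and still needs correcting. The near matches remain guesses about the origin.

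It is also fair that 40 enrolled is no sensible alternative target. The study plans responder rates, correlations and safety summaries by patient factor, which so few patients would serve badly. That is a reason to keep 130, not a derivation of 87.

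**Conclusion.** The concern holds, as a minor point: the statement is wrong as written. On the inputs printed with it, the requirement is 27 evaluable patients (25 by normal approximation) against 87 stated, and power at 87 is above 0.99 against 0.80 stated. This assumes a one-sample t-test of the change against zero with 23.8 as the SD of the change; the other standard readings tried also miss 87.

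The documents do not settle whether the number or the written criterion is wrong. Relative to the written criterion the discrepancy is conservative. For assumed SDs up to 40, the number needed stays below 87. No decision rule depends on the 0.80, so the study's conclusions are not at risk.

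**What to change.** Keep 130 and correct the rationale in section 9.5.

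- **(a) Preferred.** Retrieve the original calculation and state what it used: test, null value, target change, and SD or precision target.
- **(b) If it cannot be retrieved.** Correct 87 and give an explicit reason for 130, labelled as a later justification and not as the original basis. For example:

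> The original calculation could not be recovered; the following justification was added later. Assuming an SD of 23.8 for the change and a one-sample t-test against zero, 27 evaluable patients give 80% power for 13.4 points. The target of 130 enrolled is retained because it is expected to give about 88 evaluable patients in the observed-case analysis, with power above 0.99 for 13.4 points, 80% power for about 7.2 points, and a 95% CI half-width of about 5 points. Power for 13.4 points is about 0.87 if the SD is as large as 40.

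The cost is a change of wording in section 9.5. Enrolment, endpoint and analysis are unaffected.
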